## 6.8. Safety Monitoring

During the course of the trial, safety data will be reviewed by the DMC. This will include safety data for SAEs as stated in Sections 6.4-6.7. The DMC will, if appropriate, make recommendations regarding continuation of the trial or modification of the trial protocol. The Trial Steering Committee (TSC) will have ultimate responsibility for deciding whether the trial should be stopped on safety grounds.

#### 6.9. Development Safety Update Reports

The CI will submit (in addition to the expedited reporting above) Development Safety Update Reports (DSURs) annually throughout the trial, or on request to the Competent Authority, Ethics Committee, Host NHS Trust and Sponsor.

#### 7. Statistical Considerations

#### 7.1. Sample Size / Power Calculations

For the primary outcome of time to extubation, assuming 90% power and two-sided 5% level of significance, a log rank test with a sample size of 70 babies (35 in each arm) would be required to detect a HR of 2.3 when the control group hazard rate is 1.0. This HR is the lower end of the confidence interval found by our retrospective study; adjusted HR 6.24 (95% CI 2.34 to 16.63). This sample size will allow the detection of a clinically important absolute risk reduction of 36% for the secondary outcome of failure to extubate by day 7, with 90% power, a two-sided 5% level of statistical significance, and a control group incidence of 80%, (consistent with control group event rates reported in previous trials). As other previously published randomised trials of dexamethasone report failure to extubate by day 7 as a primary outcome, we consider this an important secondary outcome to consider in the sample size calculations.

Since all centres routinely collect the required data we anticipate a negligible loss to follow-up. However, as the primary analysis will be per-protocol, babies will be censored for the primary outcome (and other time-to-event outcomes) if the baby either dies, discontinues treatment before extubation, or remains intubated at day 16 (last day of the intervention period). These babies will be excluded from the analysis of other secondary outcomes.

Studies and published data sets show that 13.5–18% of babies <30 weeks' gestational age will have late onset sepsis, 2,18 7% will be treated for NEC,1 and 14% will be treated for PDA with cyclooxygenase inhibitors. We estimate that a third of late onset sepsis, half of NEC and a quarter of treated PDA would occur in the study period. We therefore expect that up to 14% of babies will permanently discontinue the study treatment for clinical reasons. We estimate that 10% of babies will either die before extubation, or remain intubated at day 16. These deaths will be reported to the DMC who will monitor for any safety imbalances or differences in censoring rates between the groups. The per-protocol analysis will therefore censor or exclude approximately 23% of all babies giving a final overall sample size target of at least 90 babies.

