# 2. Trial Objectives

Objectives	Outcome Measures	Timepoint(s) of evaluation of this outcome measure (if applicable)						
Primary Objective								
To determine if treatment with very low dose dexamethasone facilitates the extubation (for more than 24 hours) of ventilator dependent preterm babies of less than 30 weeks' gestation who are at high risk of developing BPD.	Time to first extubation after first IMP dose when the baby remains extubated for more than 24 hours.							
Secondary Objectives								
To determine if the treatment of ventilator dependent preterm babies of less than 30 weeks' gestation who are at high risk of developing BPD with very low dose dexamethasone impacts upon:								
1. Time to first extubation (whether or not more than 24 hours)	Time to first extubation after first IMP dose (whether or not more than 24 hours)							
2. Extubation by day 7	

(a) Extubation by day 7 (where the baby has remained extubated for more than 24 hours)

(b) Extubation by day 7 (whether or not more than 24 hours)

	Day 7						
3. Survival to 36 weeks' postmenstrual age	Alive at 36 weeks' PMA (or discharge home if sooner)	36 weeks' PMA (or discharge home if sooner)						
4. Respiratory morbidity to 36 weeks' PMA	(a) Total duration of invasive ventilation	36 weeks' PMA (or discharge home if sooner)						

Objectives	r					
(or discharge home if sooner)	through endotracheal tube  (b) Total duration of non-invasive respiratory support through nasal CPAP, nasal ventilation or high flow oxygen therapy  (c) Open-label treatment using local unit policy i.e. escalation of corticosteroid therapy or requirement for repeated courses of corticosteroid.  (d) Use of diuretics using local unit policy  (e) Total duration of supplemental oxygen therapy  (f) Severity of BPD at 36 weeks' PMA (or discharge home if sooner) as defined in Appendix 1. Oxygen requirement will be determined using the oxygen reduction test (see Appendix 2).					

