### 7.3. Statistical Analysis

Demographic factors, clinical characteristics, and service utilisation will be summarised with counts (percentages) for categorical variables, mean (standard deviation (SD)) for normal distributed variables or median (interquartile or other percentile range) for other continuous variables.

Comparative statistical analysis will entail calculating the HR plus 95% confidence interval (CI) for the primary outcome, the risk ratio (plus 95% CI) for dichotomous outcomes, and mean or median difference (plus 95% CI), for other continuous variables. Since this is an efficacy study, for the primary analysis, babies will be analysed on a per-protocol basis, excluding babies who are discontinued from the study treatment. For the primary outcome events will be censored for babies who discontinue or die before extubation or who remain intubated at day 16.

A secondary analysis will analyse all outcomes on an intention-to-treat basis. The consistency of the effect of dexamethasone will be explored to see whether it is of particular help to specific subgroups of babies, using the statistical test of interaction. The following pre-specified subgroups will be examined for the primary outcome (1) gestational age, (2) singleton vs. multiple pregnancy and (3) diuretic use at trial outset.

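### In the primary per-protocol analysis, section 7.1 drops babies from the secondary outcomes because of death, stopping treatment or intubation at day 16, so day-7 extubation, survival and open-label use are compared in babies selected on those outcomes

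*Protocol*

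**What the plan says.** Protocol section 7.1 makes the primary analysis per-protocol. A baby is censored for the primary and other time-to-event outcomes "if the baby either dies, discontinues treatment before extubation, or remains intubated at day 16". The next sentence deals with everything else: "These babies will be excluded from the analysis of other secondary outcomes". The outcomes affected are the non-time-to-event secondary outcomes in section 2: both forms of extubation by day 7, survival to 36 weeks' PMA, respiratory morbidity and the safety outcomes. Respiratory morbidity includes item 4(c), "Open-label treatment using local unit policy i.e. escalation of corticosteroid therapy or requirement for repeated courses of corticosteroid".

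Section 7.3 describes the primary analysis differently: "babies will be analysed on a per-protocol basis, excluding babies who are discontinued from the study treatment". It mentions death and intubation at day 16 only as reasons for censoring the primary outcome. It then adds: "A secondary analysis will analyse all outcomes on an intention-to-treat basis".

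Two other statements matter. Section 4.7 gives need for open-label corticosteroid as an example of a reason for stopping trial medication, and requires data collection to continue after stopping. Section 7.1 expects negligible loss to follow-up and asks the DMC to watch for imbalances in safety and in censoring between the groups.

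**The concern.** Death, stopping treatment and prolonged intubation all happen after randomisation, and treatment may affect each of them. Removing babies on that basis breaks the randomised comparison. Here the removal is also tied directly to the outcomes analysed, and missing data do not force it, because these babies remain under observation.

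At stake is the leading estimate for survival, for the safety outcomes and for failure to extubate by day 7. Section 7.1 calls the last of these important and gives it its own power statement. If dexamethasone shortens intubation, the control arm loses more babies for being intubated at day 16. If it affects early death in either direction, those deaths leave the leading survival comparison.

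**Working it through.** **The plan's own figures (section 7.1).** Up to 14% discontinue and 10% die before extubation or stay intubated at day 16.
- Combined loss: 1 − (1 − 0.14)(1 − 0.10) = 22.6%, against about 23% stated.
- Sample size: 70 / (1 − 0.226) = 90.4, against at least 90 stated.
- Day-7 failure of 80% vs 44% with 35 per arm: power 89.1% by the normal test of two proportions, against 90% stated.

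The plan's arithmetic reproduces. The fault is in the exclusion rule.

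**What the rule does to each outcome.**
- *Extubation by day 7.* A baby intubated at day 16 with no earlier extubation has failed at day 7. The rule takes certain failures out of numerator and denominator.
- *Survival.* As an illustration with assumed rates, let deaths before extubation be 10% vs 5%, and later deaths 5% of the remainder in each arm. True survival is 0.90 × 0.95 = 85.5% vs 0.95 × 0.95 = 90.3%. With the early deaths removed it is 95% vs 95%. Swapping the arms hides a harm in the same way.
- *Open-label steroid.* Babies stopped before extubation for this need are removed. Use after extubation or after the intervention period still counts, so the selection is partial.
- *Safety.* Section 7.1 attributes the expected 14% to sepsis, NEC and treated PDA. Sepsis and NEC are themselves listed safety outcomes.

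**Size for day-7 failure at the plan's 10%.** Take all removed babies as day-7 failures and let a fraction x of an arm be removed. The failure rate p among those kept becomes (p − x)/(1 − x). Power assumes 47 per arm (94 babies), less 14% discontinuing (47 × 0.86 = 40.4), less x. The split of the 10% between arms is an assumption.

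| Removed, control / dexamethasone | Control | Dexamethasone | Difference | Power |
|---|---|---|---|---|
| 10% / 10% | 0.70/0.90 = 77.8% | 0.34/0.90 = 37.8% | 40 points | about 95% |
| 15% / 5% | 0.65/0.85 = 76.5% | 0.39/0.95 = 41.1% | 35 points | about 88% |
| 20% / 0% | 0.60/0.80 = 75.0% | 0.44/1.00 = 44.0% | 31 points | about 77% |

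Without this removal, 40.4 per arm at 80% vs 44% gives about 93%.

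**Size under an assumed constant hazard.** The proportion intubated at day 16 is then the day-7 proportion raised to 16/7.
- Control: 0.80^(16/7) = 60.0%. Dexamethasone: 0.44^(16/7) = 15.3%. The average is 37.7%, against the plan's 10%.
- Day-7 failure among those kept: (0.800 − 0.600)/0.400 = 50% vs (0.440 − 0.153)/0.847 = 34%, a difference of 16 points, with power about 19%.
- If the hazard doubles or triples after day 7, the differences are 23 and 27 points (power about 40% and 58%), with averages of 25% and 18% still intubated.
- Matching the plan's 10% needs a rise of about 4.9-fold. The difference is then 31 points and power about 78%.

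**Sections 7.1 and 7.3 side by side.** Under 7.1, deaths before extubation and babies intubated at day 16 leave the secondary outcomes. Under 7.3 they stay, and only discontinued babies leave. Section 7.1 limits discontinuation to the time before extubation, and 7.3 does not. These are different analysis sets.

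**The case against.** The strongest reply is that unselected comparisons are already planned. A reader might infer that survival, day-7 extubation and open-label use are compared only in selected babies, or that an effect on early death can never show. The documents do not support either inference: section 7.3 commits to intention-to-treat for all outcomes, and the DMC monitors deaths and differences in censoring. What remains is the ranking. The selected estimate leads, and monitoring does not correct an estimate.

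A reader might also infer that the rule always shrinks the day-7 effect, or cuts its power to about 20%. That holds only under the constant-hazard assumption, which conflicts with the plan's 10%. At 10%, equal removal enlarges the contrast.

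Read literally, the wording on death in 7.1 could remove every death and make survival 100% in both arms. This is unlikely to be meant: the 10% estimate in 7.1 and the censoring rule in 7.3 both refer to death before extubation. The wording should still be made unambiguous.

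Finally, 7.3 may be the governing rule, since it is the analysis section. In that case the removal for death and day-16 intubation disappears, but discontinued babies are still dropped, and 7.1 states the wider rule without qualification. The stated rationale, that this is an efficacy study, may explain a per-protocol set defined by treatment received. It does not justify one defined by death or intubation status.

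**Conclusion.** The point holds for the primary per-protocol analysis of the secondary outcomes that are not time-to-event. Time to first extubation is censored rather than dropped and is outside this point. Section 7.1 selects babies on, or close to, the outcomes compared, and it conflicts with 7.3.

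The size and direction of the bias are not fixed by the documents. At the plan's 10%, with all those removed taken as day-7 failures, the 36-point contrast becomes 31 to 40 points depending on the split between arms. At the unfavourable end power is about 77–78%, against 90% stated. The fall to 16 points is an illustration that rests on a constant hazard. The survival figures are likewise illustrative.

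**What to change.** - Delete the exclusion sentence in section 7.1.
- Make the already planned intention-to-treat analysis the main one for survival, extubation by day 7, open-label use, safety and the other secondary outcomes that are not time-to-event.
- For extubation by day 7, keep babies still intubated at day 7 as failures, and count death without a qualifying extubation as not extubated.
- Keep any per-protocol analysis of these outcomes as supportive, with its set defined by treatment received and not by death or intubation status.
- State one analysis-set definition and use it in both 7.1 and 7.3.

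The cost is wording. No new data are needed, because collection continues after treatment stops and the intention-to-treat analysis is already promised. Precision need not suffer: if 80% vs 44% held in all 47 per arm, power would be about 96%. That is an upper figure, since babies who discontinue may dilute the contrast.

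### Section 7.1 assumes 80% of controls are not extubated at day 7 but only 10% of all babies are dead or intubated at day 16; without an unstated rise in hazard, the 23% allowance is too small and the 90% power is unsupported

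*Protocol*

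**What the plan says.** All the inputs are in protocol section 7.1.

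- **Primary outcome.** The test is planned "assuming 90% power and two-sided 5% level of significance", and "a log rank test with a sample size of 70 babies (35 in each arm) would be required to detect a HR of 2.3". The control hazard is given as 1.0, with no time unit. No number of events is stated.
- **Day-7 outcome.** The section takes "a control group incidence of 80" per cent for failure to extubate by day 7, citing earlier trials. It says the sample size allows detection of a "clinically important absolute risk reduction of 36% for the secondary outcome of failure to extubate by day 7".
- **Censoring.** Time-to-event outcomes are censored at death, at discontinuation before extubation, or at day 16 if the baby is still intubated.
- **Allowances.** Up to 14% are expected to discontinue, built up from published sepsis, NEC and PDA rates. Then: "We estimate that 10% of babies will either die before extubation, or remain intubated at day 16". No source is given for this 10%.
- **Result.** "The per-protocol analysis will therefore censor or exclude approximately 23% of all babies", which leads to a target of at least 90. Section 3 plans to recruit 94.

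**The concern.** Log-rank power depends on events, meaning extubations seen by day 16. The section starts from 70 babies and allows for missing events only through the 23%, so 70 in effect serves as the event count. The 10% is the only allowance for babies still intubated when follow-up for this outcome stops.

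That figure is hard to reconcile with the day-7 assumption. If four in five controls are not extubated after seven days, having only one baby in ten across both arms dead or intubated nine days later requires extubation to speed up sharply. The protocol neither states nor justifies this.

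Two things depend on it. One is the stated power for the primary outcome. The other is the censoring that the DMC should expect: section 7.1 asks the DMC to watch for differences in censoring rates between the groups, and 23% would be the wrong benchmark if the true share without an event is much larger.

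**Working it through.** **1. Reproduce the plan's figures.** Two-sided 5%, 90% power, HR 2.3, 1:1 allocation.

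- Schoenfeld: 4 × (1.960 + 1.282)² / (ln 2.3)² = 60.6, so 61 events.
- Freedman: (1.960 + 1.282)² × (3.3/1.3)² = 67.7, so 68 events.
- The stated 70 agrees with Freedman if nearly every baby has an event.
- Combined loss: 1 − 0.86 × 0.90 = 22.6%, about 23%. Inflation: 70/0.77 = 90.9, against the stated 90.

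The formula and the inflation are sound. The question is whether the 10% fits the 80%.

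**2. Carry the day-7 rate to day 16 under a constant hazard.**

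- Controls: 0.80^(16/7) = 0.600.
- Treated, HR 2.3: 0.600^2.3 = 0.309.
- Mean: 0.455, before any deaths, against the stated 0.10.

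**3. What would make both figures true?** Let s be the share of controls intubated at day 16. Solving (s + s^2.3)/2 = 0.10 gives s = 0.18.

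- Control hazard over days 7–16: ln(0.80/0.18)/9 = 0.165 per day. Over days 0–7: −ln(0.80)/7 = 0.032 per day. Ratio about 5.2.
- If nobody is extubated in the first 48 hours, the early hazard is −ln(0.80)/5 = 0.045 per day and the ratio is about 3.7.
- Conversely, a constant hazard with s = 0.18 at day 16 implies 0.18^(7/16) = 47% of controls intubated at day 7, not 80%.

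**4. Events and power.** Log-rank simulation with HR 2.3, 80% of controls intubated at day 7, 14% discontinuing, censoring at day 16 and no deaths (10,000 trials per cell; Monte Carlo error about 0.4 points). Neither the hazard shape nor the timing of discontinuation is in the protocol, so both are varied as assumptions. Cells show events and power for N = 90, then N = 94.

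| Control hazard | Mean intubated at day 16 | Discontinuation all at day 0 | Discontinuation even over days 0–16 |
|---|---|---|---|
| Constant | 45% | 42, 76%; 44, 78% | 46, 80%; 48, 81–82% |
| Rises 1.5-fold after day 7 | 37% | 49, 82%; 51, 84% | 53, 85%; 55, 87% |
| Doubles after day 7 | 30% | 54, 86%; 56, 88% | 58, 89%; 61, 90% |
| None for 48 hours, then constant | 39% | 48, 82%; 50, 83% | 52, 84%; 54, 86% |
| None for 48 hours, doubles after day 7 | 23% | 60, 89%; 63, 91% | 65, 91%; 68, 93% |

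The share without an event runs from 1 − 42/90 = 53% (first row) to 1 − 68/94 = 28% (last row). All of these exceed 23%. For the first row with discontinuation at day 0, closed forms give 77–79% (Schoenfeld) and 73–74% (Freedman).

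**5. Day-7 statement, checked separately.** 80% against 44% at 35 per arm gives 89% power, close to the stated 90%. The HR matching that difference is ln 0.44/ln 0.80 = 3.7. HR 2.3 gives 0.80^2.3 = 0.60 in the treated arm, a difference of 20 points.

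**The case against.** The best defence is that the protocol never commits to a constant hazard. Babies enter only if judged unlikely to be extubated within 48 hours, so a slow start is built in, and extubation may well quicken later. With such a lag and a modest later rise, power comes back to about 90%. HR 2.3 is also cautious: section 7.1 takes it from the lower confidence limit of an estimate of 6.24. At HR 3.7 and a constant hazard, 90 babies give about 48 events and power of about 99%.

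Most of this stands, and it rules out several stronger readings.

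- A reader might infer that 90% power is wrong and the true figure is about 80%. The documents do not fix the hazard shape or when babies discontinue, so 80% is one scenario.
- A reader might compute that 131 to 146 babies are needed. That follows only from a constant hazard with all discontinuation at entry.
- A reader might call the 36-point reduction inconsistent with HR 2.3. The sentence gives a detectable difference for a separate outcome. It does not say that HR 2.3 produces 36 points, and it holds on its own inputs.
- A reader might take the control hazard of 1.0 as one per week and find a further clash. The protocol gives no unit, and 1.0 may simply be the reference for the ratio.

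The defence does not rescue the 10%. Even with the 48-hour lag, the hazard must rise 3.7-fold after day 7, and nothing in the protocol says so.

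**Conclusion.** The 80% at day 7 and the 10% at day 16 conflict unless the extubation hazard rises about four- to five-fold after the first week, which the protocol does not state. In every scenario examined, with rises up to two-fold, more than 23% of babies have no event.

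The claim of 90% power at HR 2.3 with 90 to 94 babies is therefore unsupported, not disproved. It is about 76–82% under a constant hazard. With a 48-hour lag it is about 84–86% if discontinuation is spread evenly, or 82–83% if all at day 0. If the hazard doubles after day 7 it is about 86–93%.

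These figures rest on proportional hazards, 14% discontinuing, assumed discontinuation timing and no deaths; deaths before extubation would lower the event counts further. The event formula, the inflation step and the day-7 statement are not at fault.

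**What to change.** Restate section 7.1 on one timeline:

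- Give the required number of events: 61 (Schoenfeld) or 68 (Freedman), naming the formula.
- Derive the proportion intubated at day 16, and the share without an event, from one extubation curve that passes through 80% of controls at day 7. State the hazard shape, the timing of discontinuation and the allowance for deaths as assumptions.
- Replace the 10% and the 23% with the results.
- Give power at 90 to 94 babies as the resulting range.
- Keep the 36-point day-7 statement. Optionally add that it corresponds to an HR of about 3.7, whereas the design HR of 2.3 implies about 20 points.

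The cost is a rewrite of part of one section and a less favourable power statement. The sample size, outcomes and analysis stay as they are.

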#### 7.2. Hypotheses to be tested

To determine if the treatment of ventilator dependent preterm babies of less than 30 weeks' gestation who are at high risk of developing BPD with very low dose dexamethasone impacts upon:

- i. Time to extubation (where the participant remains extubated for more than 24 hours)
- ii. Time to extubation (whether or not the participant remains extubated for more than 24 hours)
- iii. Rates of extubation by day 7 (where the participant remains extubated for more than 24 hours)
- iv. Rates of extubation by day 7 (whether or not the participant remains extubated for more than 24 hours)
- v. Survival to 36 weeks' PMA (or discharge home if sooner)
- vi. Respiratory morbidity to 36 weeks' PMA (or discharge home if sooner)
- vii. Cytokine profile
- viii. Safety outcomes
- ix. Parent/family experience

### 7.3. Statistical Analysis

Demographic factors, clinical characteristics, and service utilisation will be summarised with counts (percentages) for categorical variables, mean (standard deviation (SD)) for normal distributed variables or median (interquartile or other percentile range) for other continuous variables.

Comparative statistical analysis will entail calculating the HR plus 95% confidence interval (CI) for the primary outcome, the risk ratio (plus 95% CI) for dichotomous outcomes, and mean or median difference (plus 95% CI), for other continuous variables. Since this is an efficacy study, for the primary analysis, babies will be analysed on a per-protocol basis, excluding babies who are discontinued from the study treatment. For the primary outcome events will be censored for babies who discontinue or die before extubation or who remain intubated at day 16.

A secondary analysis will analyse all outcomes on an intention-to-treat basis. The consistency of the effect of dexamethasone will be explored to see whether it is of particular help to specific subgroups of babies, using the statistical test of interaction. The following pre-specified subgroups will be examined for the primary outcome (1) gestational age, (2) singleton vs. multiple pregnancy and (3) diuretic use at trial outset.

Basic cytokine data analysis will be largely conducted using a combination of Kruskal-Wallis and post hoc Dunn's tests. Significance levels will be corrected for multiple comparisons by applying Holm's sequentially selective Bonferroni method. Thereafter, correlation, principal components and factor analyses will be used as recognised tools to investigate mediator interrelationships. More informative network-based approaches will be used to model inflammatory cytokine:cytokine network interactions using Bayesian methods refined in-house. These networks offer a framework combining uncertainty (probabilities) and logical structure (independence constraints) to represent complex biological phenomena by generating acyclic graph-based models of joint probability distributions representing the conditional independence between related variables. The key element of this approach is that this allows investigators to capture the complex biological features of cytokines such as antagonism, synergy and functional redundancy, as we have recently shown (Field et al., BMC Systems Biology, In Press) rather than relying on the increasingly inadequate T helper cell type 1/2 (Th1/Th2) paradigm.

Two dichotomisations will be applied: one in response to dexamethasone therapy versus placebo and one relating to the time to extubation (groupings for the latter will be determined empirically based on the data emerging from the study), independent of treatment. Both will incorporate a dynamic aspect to the Bayesian model to account for changes in cytokine profiles and interrelationships over time. Data from each group will also be used to develop modified variational Bayesian state space models (where we will also use the human-specific text learning algorithm (https://compbio.dfci.harvard.edu/predictivenetworks/) to generate prior networks. Initialisation fields will be set to 10 seeds and 1,000 iterations, and the maximum hidden state dimension limited to 20. A z score equivalent to a 98% significance threshold will be used to define the number of edges reaching significance. Networks will be visualised using either Cytoscape or the open graph Viz platform Gephi. The spatialisation technique applied will be the force-directed Yifan Hu algorithm, whereas a community detection algorithm will be used to detect the underlying graph topology modular structure. We also plan to use machine learning-based methods in an attempt to identify the value of specific small groups of cytokines as predictors of outcome by using a support vector machines and random forest-based combinatorial approach developed in-house. The main focus of these will be to offer a starting point for an iterative stepwise empirical identification of outcome predictors based on feature importance ranking. Further modelling will be performed according to the manifestation of BPD as a secondary outcome measure.

